# **11.5. NONSERIOUS ADVERSE EVENT**

• Non-serious Adverse Events (AE) will be provided to BMS as part of an annual reporting requirement.

A non-serious adverse event is an AE not classified as serious.

## Non-serious Adverse Event Collection and Reporting

The collection of non-serious AE information will begin at initiation of study drug. All non-serious adverse events (not only those deemed to be treatment-related) will be collected continuously during the treatment period and for a minimum of 30 days following the last dose of study treatment.

Non-serious AEs should be followed to resolution or stabilization, or reported as SAEs if they become serious. Follow-up is also required for non-serious AEs that cause interruption or discontinuation of study drug and for those present at the end of study treatment as appropriate.

# 11.6. Laboratory Test Abnormalities

All laboratory test results captured as part of the study will be recorded following institutional procedures. Test results that constitute SAEs will be documented and reported to BMS as such at the discretion of the PI in accordance with standard of care practice.

The following laboratory abnormalities will be documented and reported appropriately:

- any laboratory test result that is clinically significant or meets the definition of an SAE
- any laboratory abnormality that required the participant to have study drug discontinued or interrupted
- any laboratory abnormality that required the subject to receive specific corrective therapy.

It is expected that wherever possible, the clinical rather than laboratory term would be used by the reporting investigator (eg, anemia versus low hemoglobin value).

# 11.7. Potential Drug Induced Liver Injury (DILI)

Specific criteria for identifying potential DILI have not been identified for this protocol. Standard medical practice in identifying and monitoring hepatic issues will be followed.

# 11.8. Overdose

An overdose is defined as the accidental or intentional administration of any dose of a product that is considered both excessive and medically important. All occurrences of overdose will be reported as an SAE.

#### 11.9. Other Safety Considerations

Any significant worsening noted during interim or final physical examinations, electrocardiograms, X-rays, and any other potential safety assessments, whether or not these procedures are required by the protocol, should also be recorded as a non-serious or serious AE, as appropriate, and reported accordingly.

# 12. STATISTICAL ANALYSIS

12.1. Overview. This is a pilot study to evaluate the changes in FDG myocardial uptake postbiologic treatment of RA patients with abatacept vs adalimumab. Summary statistics for outcomes and predictor variables will be examined; with comparisons made using student t-test and Wilcoxon rank-sum test for normally and non-normally distributed continuous variables, respectively. Counts and percentages will be calculated for categorical variables and compared using the chi-square or Fisher's exact test, as appropriate. In Aim 1, using generalized estimating equations (GEE), models will be constructed to explore the association between treatment arms (abatacept vs adalimumab) and change in myocardial FDG uptake treated as a continuous variable (measured by SUV units). Similarly, linear mixed effects models will be used to define the association between T cell subpopulations and myocardial FDG uptake per treatment arm strata. Given the small sample size of the study, we will not have the power to adjust for multiple variables, but the two treatment arms will be matched for age, sex, and disease activity, and the contribution of RA-disease characteristics and traditional CVD risk factors to the variability of myocardial FDG uptake will be ascertained. All statistical calculations will be performed using SAS 9.4. In all tests, a 2-tailed  $\alpha$  of 0.05 will define statistical significance.

**12.2. Sample Size and Power Analysis.** Data on what is considered a significant change in myocardial FDG uptake in RA is not yet known. Hence, based on our preliminary data that included only 8 patients on abatacept, and as a proof of concept, for the proposed pilot

studies we will include 10 patients in the abatacept arm and compare them with 10 patients on adalimumab. Through normal approximation using the Z statistic, with a SD of 0.5 in the SUV units of myocardial FDG uptake seen in the RHYTHM study, we will have 80% power to detect an effect size of 0.6 between the groups, at an alpha level of 0.05.

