#### 2.RATIONALE.

**2.1.** *Preliminary Data.* In a single RHeumatoid arthritis studY of THe Myocardium (RHYTHM study), a total of 119 RA patients without clinical CVD underwent cardiac FDG-PET/CT, with myocardial inflammation assessed qualitatively and quantitatively by visual inspection and by calculation of the standardized-uptake-value (SUV) units. Qualitative myocardial FDG uptake was observed in 39% of the patients (Figure 1). By quantitative assessment, the median

myocardial SUV mean was 1.9 (inter-quartile range [IQR]: 1.5-2.6), and the median SUV max was 3.0 (IQR: 2.1-4.5).

**Figure 1.** Example of diffuse Myocardial F-FDG uptake Scan in an RA patient. Short Axis for a, b and c; horizontal axis for d; and vertical long axis for e.

As expected, RA patients with visually detected FDG uptake had higher SUVs by quantitative assessment than patients without visually detected FDG uptake (median SUV mean of 2.8 [IQR: 2.2-4.9] vs 1.6 [IQR: 1.4-1.9], p <0.0001), and median SUV max of 4.9 [IQR: 3.6-9.4] vs 2.3 [IQR 2.0-2.9], p < 0.0001, respectively). Interestingly, when comparing the degree of myocardial FDG uptake in RA patients on abatacept vs no biologic agents; abatacept treatment (n=8) was associated with a lower SUV mean. This association remained statistically significant with an 18% lower myocardial SUV mean seen after adjusting for disease activity (Clinical Disease Activity Index less vs greater or equal to 10) (beta=-0.36) (Figure 2). No significant difference was seen between myocardial FDG uptake in those on non-biologic DMARDs vs TNF-inhibitors (p=0.69). In addition, higher CDAI and DAS-28 scores, non-Hispanic black race, and body mass index (BMI) were significantly associated with a higher SUV mean. A CDAI ≥10 (moderate/high disease activity) was associated with a 0.31 increase in SUV mean when compared to the group with CDAI in remission or low disease activity (CDAI<10) (beta=0.31, p=0.006). A similar relationship was observed with DAS-28. Non-Hispanic black RA patients had 22% higher SUV mean than non-Hispanic whites (beta=0.31, p=0.006). However, in adjusted analyses, only the CDAI≥10 remained significantly associated with a higher SUV mean.

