#### **3.STUDY OBJECTIVES**

The aim of this study is to evaluate the effects on myocarditis in rheumatoid arthritis (RA) of abatacept, a CTLA4-Ig fusion protein that binds CD80/86 (B7-1/B7-2).

**3.1. Primary Objective.** Compare the change in myocardial FDG uptake in RA patients treated with abatacept vs adalimumab. Rationale: In murine models, CD40L/B7-1 and CTLA4 blockade decreases myocardial inflammation, damage and mortality. Additionally, our pilot data suggests that lower myocardial FDG uptake in seen in RA patients on abatacept compared with other DMARDs. Approach: Using FDG PET cardiac imaging to identify myocardial inflammation at baseline and post-treatment, we will quantitatively compare the change in myocardial FDG uptake in biologic naïve RA patients without clinical CVD and with inadequate methotrexate response, following randomization to 16-week treatment with abatacept vs the TNF-inhibitor adalimumab. Conventional CVD risk factors and measures of RA disease activity and severity will be ascertained.

**3.2. Secondary Objective.** Identify T cell subpopulations associated with myocardial FDG uptake in RA patients treated with abatacept vs adalimumab. Rationale: Reflecting the adaptive immune response underlying RA, the proportion of peripheral T cell subsets in RA patients significantly differs from normal controls. These include differentiation to memory effector subsets, acquisition of NK receptors, exhaustion markers, and enhanced inflammatory cytokine expression. Furthermore, T cell lymphocytic infiltration has been described in autoimmune myocarditis resulting as a complication of CTLA4 immune checkpoint inhibition. These data suggest a role for T cell subsets in the pathogenesis of myocarditis in RA with potential differences depending on mechanism of action of the DMARD. Approach: We will test whether elevations in different T cell subsets are associated with myocardial FDG uptake in RA patients treated with abatacept vs adalimumab. Subsequently, the transcriptional phenotype of candidate subpopulations isolated by cell sorting will be comprehensively delineated by low cell input RNAseq to define the specific immunobiologic characteristics of these particular cellular subsets that are mechanistic candidates to mediate myocardial inflammation.

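### The 80% power in Section 12.2 rests on an SD of 0.5 credited to RHYTHM, which the RHYTHM figures in Section 2.1 do not support, and no SD of change is given

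*Combined protocol and SAP*

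**What the plan says.** Section 12.2 fixes the size at 10 patients per arm as a proof of concept, "based on our preliminary data that included only 8 patients on abatacept". It uses a normal approximation with the Z statistic and takes its SD from RHYTHM: "with a SD of 0.5 in the SUV units of myocardial FDG uptake seen in the RHYTHM study, we will have 80% power". The full claim is: "we will have 80% power to detect an effect size of 0.6 between the groups, at an alpha level of 0.05". Section 12.1 makes all tests two-tailed.

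The primary objective (Section 3.1) is to "Compare the change in myocardial FDG uptake in RA patients treated with abatacept vs adalimumab", from baseline to week 16. Section 5.4 derives two measures, SUV mean and SUV max. Section 12.2 does not say which one the power refers to.

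Section 2.1 describes RHYTHM (119 patients) by medians and quartiles of uptake only:

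- Whole sample: "myocardial SUV mean was 1.9 (inter-quartile range [IQR]: 1.5-2.6"; SUV max median 3.0 (2.1 to 4.5).
- "Qualitative myocardial FDG uptake was observed in 39% of the patients".
- With versus without visual uptake: "median SUV mean of 2.8 [IQR: 2.2-4.9] vs 1.6 [IQR: 1.4-1.9" and "median SUV max of 4.9 [IQR: 3.6-9.4] vs 2.3 [IQR 2.0-2.9".

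No SD, SD of change or repeat-scan correlation is reported. Section 1.1.2 says that data on the response of myocardial uptake to DMARDs in RA are lacking.

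**The concern.** The SD drives the power statement, and the reader is told that it was observed in a named study. The figures reported from that study look far more dispersed than 0.5. About a tenth of the patients (a quarter of 39%) have an SUV mean of 4.9 or more, while about three quarters of the larger group are at 1.9 or less.

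The analysis also concerns change between two scans. Its SD depends on the single-scan SD and on the correlation between scans, and the protocol does not report that correlation.

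The 80% is the protocol's only statement of what 20 patients can detect. If its basis is unclear, a null result cannot be interpreted, and a later, larger trial may inherit an SD that nobody can trace.

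**Working it through.** **1. The plan's own figure.** Inputs: n = 10 per arm, SD 0.5, two-sided alpha 0.05, difference 0.6 read as raw SUV units.

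- SE = 0.5 × √(2/10) = 0.2236.
- Z method: 0.6/0.2236 − 1.96 = 0.723, so power = Φ(0.723) = 76.5%.
- Difference detectable with 80% power: (1.960 + 0.842) × 0.2236 = 0.626, which prints as 0.6. Rounding explains the gap.
- Two-sample t-test (noncentral t, 18 df): 72%. Power of 80% needs a difference of 0.66.
- If 0.6 were a standardised effect, power would be 27%, so the raw reading is the one intended.

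**2. Smallest SD that the RHYTHM quartiles allow.** Each subgroup is cut at its quartiles into four cells. Each cell is placed at the point nearest the overall mean that its limits permit. This gives the minimum variance without assuming any distribution. For SUV mean (weights 0.39 and 0.61) the minimum is reached at a mean of about 2.28:

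| Cell | Weight | Placed at | Weight × squared distance |
|---|---|---|---|
| Uptake, Q1 | 0.0975 | 2.2 | 0.0007 |
| Uptake, Q2 | 0.0975 | 2.28 | 0 |
| Uptake, Q3 | 0.0975 | 2.8 | 0.0260 |
| Uptake, Q4 | 0.0975 | 4.9 | 0.6675 |
| No uptake, Q1 | 0.1525 | 1.4 | 0.1190 |
| No uptake, Q2 | 0.1525 | 1.6 | 0.0712 |
| No uptake, Q3 | 0.1525 | 1.9 | 0.0224 |
| No uptake, Q4 | 0.1525 | 2.28 | 0 |

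The sum is 0.907, so the SD is at least √0.907 = 0.95. If every quartile is off by 0.05 through rounding, the floor is 0.92. If whole-patient counts (46 or 47 with uptake) are also allowed for, it is 0.90. For SUV max the floor is 2.03 at face value and 1.96 with both allowances. Within the visual-uptake group alone, the SUV mean floor is 0.93 with both allowances. In the group without visual uptake it is only 0.14, so an SD of 0.5 is possible there.

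**3. SDs implied by the IQRs under normality (IQR/1.349).**

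| | All | With uptake | Without uptake |
|---|---|---|---|
| SUV mean | 1.1/1.349 = 0.82 | 2.7/1.349 = 2.00 | 0.5/1.349 = 0.37 |
| SUV max | 2.4/1.349 = 1.78 | 5.8/1.349 = 4.30 | 0.9/1.349 = 0.67 |

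None is 0.5. The only spread of 0.5 in Section 2.1 is the width of the SUV mean IQR without visual uptake (1.4 to 1.9). That is a width, not an SD, and Section 6 does not restrict entry to such patients.

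**4. From single scan to change.** With equal SDs at both scans, SD of change = SD × √(2(1 − r)). The baseline-adjusted SD is SD × √(1 − r²), with 17 df. The correlations r are assumptions. T-test power for 0.6, 10 per arm:

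| Single-scan SD | Analysis | r = 0.5 | 0.7 | 0.8 | 0.9 |
|---|---|---|---|---|---|
| 0.95 | Change score | 27% | 41% | 56% | 85% |
| 0.95 | Baseline-adjusted | 34% | 46% | 60% | 86% |
| 0.5 | Change score | 72% | 91% | 98% | >99% |
| 0.5 | Baseline-adjusted | 83% | 94% | 99% | >99% |

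An SD of change of 0.5 needs r = 1 − 0.25/(2 × SD²). That is 0.86 for a single-scan SD of 0.95, 0.85 for 0.90 and 0.50 for 0.5. For SUV max with an SD of 2.0 it is 0.97.

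**5. Precision and power by SD of change.** The 95% CI half-width is 2.101 × SD × √(2/10).

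| SD of change | Power for 0.6 (t-test) | CI half-width (SUV) |
|---|---|---|
| 0.5 | 72% | 0.47 |
| 0.7 | 44% | 0.66 |
| 0.95 | 27% | 0.89 |

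**The case against.** The strongest reply is that Section 12.2 contains no arithmetic error of substance and that nothing refutes 0.5 outright. The floor of 0.90 applies to single-scan SUV mean across all 119 patients, and Section 12.2 never says that 0.5 is that quantity. It could be the SD in the 8 abatacept patients, a residual SD, or a value in Figure 2, which was not available for this review. All of this stands. It limits the point to an unsupported and undefined input and leaves the direction of the error open.

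A second reply is that baseline adjustment raises power. The synopsis says the GEE models take baseline uptake into account, although Section 12.1 omits that phrase. This is fair, and the adjusted rows are shown above. They do not settle the matter, because they depend on the same unstated correlation.

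A third is that the measure is less ambiguous than claimed, since the abatacept comparison in Section 2.1 is on SUV mean. That makes SUV mean the likely choice, but Section 12.2 should say so.

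A fourth is that this is a pilot with frank caveats. Section 12.2 says that a significant change is not yet known, and Section 5.8 admits that the sample size may under- or overestimate it. Those caveats concern the size of change that matters clinically, not the SD. They lower the stakes without answering the point.

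**Conclusion.** The concern holds. The SD of 0.5 cannot be the whole-sample RHYTHM SD of SUV mean (at least 0.90) or of SUV max (at least 1.96). It matches no SD reported in Section 2.1 or derivable from its IQRs under normality. No SD of change or correlation supports it for the primary objective.

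The floors rest only on the published quartiles and the 39%. The power ranges rest on assumed correlations and equal SDs at both scans. Power for 0.6 could be well below or well above 80%, so this is not a finding that the trial is underpowered. Even if the SD of change is taken as 0.5, the t-test benchmark for 20 patients is 72%, not 80%.

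The choice of 10 per arm can stand as a pilot size. The stated power and its attribution should be corrected.

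**What to change.** Keep the 20 patients, the objectives and the tests. In Section 12.2:

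1. Restate the power, for example: *10 patients per arm give 72% power (two-sided t-test, alpha 0.05) for a 0.6 SUV difference in change if the SD of change is 0.5, and 80% power for 0.66; this is a t-test benchmark for the planned GEE.*
2. State which patients, which SUV measure and which type of value (single scan or change) the 0.5 describes, or remove the attribution to RHYTHM.
3. Add one sensitivity line: for assumed SDs of change of 0.5, 0.7 and 0.95, power for 0.6 is 72%, 44% and 27%, and the 95% CI half-width is 0.47, 0.66 and 0.89 SUV.

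The cost is two sentences and one line. No patients, endpoints or tests change. The only drawback is a less favourable stated power.

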# 13. OTHER AND ADMINISTRATIVE CONSIDERATIONS

# 13.1. Data Management

For data collection and management purposes, subjects will be identified by a subject number only. All collected data will be transferred to a database exclusively using the SID only. The raw information for input into the database will be stored in binders in a locked cabinet in the PI's office. The database will be saved in an encrypted computer and backed up onto an encrypted portable hard drive on a weekly basis, and the backups also kept in the locked cabinet. Hardcopy files will be stored in a locked cabinet in a locked room. Only the Principal Investigator and study staff will have access to these files. Those with access are held to the strictest standards of confidentiality. Data reported on the database must be consistent with the source data or the discrepancies must be explained. When needed, copies of supported documentation such as medical records current and/or previous should be requested and filed prior de-identification. All data must be derived from source documents.

# 13.2. Confidentiality

The confidentiality of participating subjects will be maintained. Subjects will be individually assigned a unique coded identification number The data file and the file that links the unique subject number to patient identity will be maintained separately in password protected files on password protected and fully encrypted computers in a locked office in the Division of Rheumatology. Hard-copy files will be stored in a locked cabinet in a locked room. Those with access are held to the strictest standards of confidentiality. Documents that identify the subject beyond subject number will not be released outside of Columbia University Medical Center and/or New York-Presbyterian Hospital (e.g., the signed informed consent document) and will be maintained in strict confidence by the investigator, except to the extent necessary to allow auditing by the regulatory authorities, study monitor, or sponsor representatives.

Standard HIPAA procedures and guidelines will be enforced. The consent form discloses to potential participants the individuals and/or agencies that are able to look at and copy research records, namely:

- The principal investigator, co-investigators, study staff and other medical professionals who may be evaluating the study

- Authorities from Columbia University and New York-Presbyterian Hospital, including the Institutional Review Board ('IRB')

- The Office of Human Research Protections ('OHRP')

- Representatives from and or of the FDA, federal or state government agencies, other health authorities and their commercial partners.

- Information made available for inspection will be handled in strictest confidence and in accordance with local data protection laws. In addition to confidentiality disclosures described in the consent form, potential participants will also sign the attached study specific HIPAA Form before participating in this study. The consent discussion will take place in private locations (e.g. interview room; physician's office; exam room). Participants will be given an ICF including the HIPAA form providing a specific description of the ways in which their personal health information will be used and disclosed in the course of this study. The Investigators or Research staff will explain and answer all the questions participants may have regarding their privacy protection. If they decide to participate, participants will be asked to sign the combined consent and HIPAA form authorizing the use and disclosure of their personal information before starting the study.

## 13.3. Potential Risk

A risk exists that despite all provisions to maintain participant's confidentiality, confidentiality nonetheless may be compromised. As mentioned above every effort will be made to secure the data collected and separate identifying from de-identified information.

Phlebotomy is associated with minor discomfort and occasional patients may experience a more severe vaso-vagal reaction and light-headedness. A minor risk of a skin infection at the site of phlebotomy also exists but may be treated with a short course of antibiotics should it occur.

The mortality of the PET-CT imaging is low and associated mainly with the administration of adenosine/regadenoson for evaluations under stress. In patients with established coronary artery disease, mortality is reported to be 2/10000patients. The risk for an acute myocardial infarction is also reported to be 2/10000. These numbers will not be applicable to our participants as candidates with prior cardiovascular events will be screened out. Furthermore, the mortality at the Columbia University PET center has been 0% for PET-CT stress tests for the last 15 years with over 11000 PET-CT stress tests performed.

The radiation exposure/dosimetry with cardiac PET with: F18 FDG imaging is within FDA guidelines for research of this type. The radiation obtained during the PET CT-F18-FDG imaging examinations for this protocol would be 16.46 mSvs (1646 mrem) which is equivalent to about 5.4 years of natural and cosmic radiation. The patients will have to be fasting overnight when they present for their study visits and this may cause mild discomfort.

In addition, study participants will be asked if they received radiation from imaging procedures outside the current protocol (for their regular clinical care). If other imaging studies have taken place, the cumulative radiation exposure will be calculated and if it exceeds the level of 50 mSv which is considered to be the maximum acceptable radiation exposure per year then the subject will not participate in the study.

The testing performed in this study may unmask conditions that have been silent (asymptomatic). If a significant medical finding is noted during participation in this study, the PI will be notified immediately by the nuclear cardiologist, study personnel or the PET-CT center.

#### 13.4. Potential Benefit

There are no direct benefits anticipated for the participating subjects. However, evaluating RA patients for early and potentially cardiac reversible changes such as the presence of myocardial inflammation will offer insight into the pathophysiology driving this disorder and guide an early intervention when warranted. The findings derived from this study could benefit the society by having multidisciplinary implications that could lead to the prevention of clinical vascular events and improvement in survival in patients with RA.

